## Introduction

Treatment for edentulous patients is either removable complete or partial dentures. However, the use of removable dentures reduces taste perception and chewing capacity. Dental implants have become a predictable treatment option for applicable patients. The success rate of dental implants is associated with bone quality and quantity.

Most implant failures occur in the maxillary molar region with poor bone quality. Other factors that may cause failure and difficulty in implant placement in the posterior maxilla are limited visibility, reduced inter-arch space, and sinus pneumatization due to atrophy of the alveolar ridge. In such cases, sinus augmentation is required to create sufficient vertical bone volume for implant placement with adequate stability.

Numerous methods have been proposed to treat a vertically deficient, edentulous, posterior maxillary ridge of poor bone quality. Traditionally, two techniques are employed, namely, the direct sinus elevation procedure using a lateral window approach and the indirect sinus elevation procedure using a crestal approach. The lateral window approach has been reported to yield predictably favorable clinical results. Nonetheless, the degree of invasiveness and patient morbidity, risk of severing the alveolar antral artery, risk of perforating the sinus membrane, delay in healing, and increased risk of postsurgical infection are major drawbacks of this procedure. Conversely, the transcrestal indirect sinus elevation techniques are less invasive, less time-consuming, and reduce patient morbidity. However, the risk of membrane perforation may be as high as 24% due to lack of direct visibility and access.

Many surgical techniques have been developed to lift the sinus membrane indirectly, Summers in 1994 had described a technique; the Osteotome sinus Floor Elevation (OSFE) wherein an osteotome is used to fracture the sinus floor and to lift the sinus membrane, then grafting materials and implants can be inserted in the subantral space through the osteotomy site.  This technique also is not without its drawbacks, namely, explosive force to the maxilla with poor control, unintentional displacement or fracture, membrane perforation, benign paroxysmal positional vertigo and patient discomfort. 

Vercellotti et al presented the use of piezoelectric ultrasound as a new alternative in performing osteotomies in maxillary sinus lifting surgeries.  An important feature of the piezoelectric device is the selective cutting of only mineralized structures, without damaging soft tissues.  No perforations of the Schneiderian membrane occurred during the piezoelectric preparation of the lateral anrostomies.  Piezosurgery was used to expose the maxillary sinus mucosa through the alveolar crest pathway in maxillary sinus floor elevation with hydraulic pressure for the graft and simultaneous implant placement. Some potential advantages of the method are reduced trauma and a reduced rate of sinus membrane perforation during surgery, no malleting, and shorter surgery time. Although all of these advantages, membrane perforation by high hydraulic pressure may happens. 

An additional technique of bone instrumentation called osseous densification was introduced. It is a biomechanical osteotomy preparation technique that preserves bone through a non-excavating drilling process utilizing specially designed drills with a tapered geometry and specially designed flutes to progressively expand the osteotomy while compacting bone into its walls and apex. In this manner, this bone densification method enhances implant primary

stability due to an elastic “spring-back” effect created in the prepared osteotomy by the compaction autografting.

In view of this, it would be of value to assess the effect of these different techniques which have been used in crestal sinus lifting compared to each other. Such comparison may aid toward further clarification of this, with aspect to overcome one of the most perplexing phenomena which is weak implant stability and low bone level associated with sinus pneumatization.

### **Aim of study**

The aim of the present study is to evaluate and compare the efficacy of different techniques for implant placement in deficient posterior maxilla

### **Objective**

Evaluation of implant primary and secondary stability, bone gain and density using different techniques (Osteotome technique, Densah drills technique, Piezosurgery) in crestal sinus lifting.

## **Patients and Methods**

### **Study design**

Comparative study

### **Study setting and population**

Twenty one patients will be included from those attending at the Department of Oral Medicine, Periodontology, Oral Diagnosis and Oral Radiology, Faculty of Dental Medicine, (Boys ,Cairo) Al-Azhar University.

### **Eligibility criteria of population:**

#### **A. Inclusion criteria:**

- (1) Young and adult patients of both sexes.
- (2) Patients exhibit class C residual bone height according to ABC sinus augmentation classification.
- (3) The edentulous ridges are covered with mucoperiosteum free from signs of inflammation, ulceration or scar tissue.
- (4) Remaining natural teeth have good periodontal tissue support.
- (5) Occlusion showing sufficient inter-arch and intra-arch spaces for future prosthesis.

#### **B. Exclusion criteria:**

- (1) Patients with systemic conditions that could influence the outcome of the therapy as: Pregnancy and Heavy smokers
- (2) Patients with systemic disease that may affect bone quality.
- (3) Uncooperative patients

- (4) Patients with active periodontal disease.
- (5) Patients with neglected oral hygiene.
- (6) Patients with limited mouth opening and unfavorable intermaxillary arch space.
- (7) Patients with maxillary sinus disease or previous sinus surgery.

### C. Ethical consideration:

All participants will be verbally informed about the nature of the study, and written informed consent will be collected for participation in the study.

### **Sample size calculation**

According to analyses of the post-operative bone height, sample size calculation was undertaken via G power version 3.1 statistical software based on the following pre-established parameters: an alpha-type error of 0.05, a power test of 0.95, a total sample of at least 21 subjects (7 subjects for each group) appeared to be sufficient.

### **Intervention**

The patients will be randomly divided into 3 equal groups:

- 1) Group 1 (controlled group): 7 patients will be treated by traditional closed sinus lift (osteotome) with bone grafting (xenograft) and implant placement.
- 2) Group 2: 7 patients will be treated by densah drills (Versah, Jackson, MI, USA) sinus lift with bone grafting (xenograft) and implant placement.
- 3) Group 3: 7 patients will be treated by piezoelectric (Piezotome; Satelec) crestal sinus lift with bone grafting (xenograft) and implant placement.

### Pre-surgical Therapy:

Before the surgery, each patient will be given careful instructions in proper oral hygiene measures. A full mouth supragingival and subgingival scaling and root planning procedure will be performed under local anesthesia using ultrasonic as well as hand instrumentation.

-Cone-beam computed tomography (CBCT) will be taken to estimate the height and width of the bone crest and bone density.

### Surgical Procedure:

Patients will be asked to use 0.12% chlorhexidine digluconate rinse, and Povidone iodine solution will be used to perform extraoral antiseptics. After administration of local anesthesia at the implant site, a full thickness flap will be elevated to expose the crest of alveolar ridge. A pilot drill will be used to start the osteotomy preparation, which should be ended 1mm short of sinus floor. **In group 1; (closed sinus lifting with Osteotome):** The drills can be sequentially used to widen the osteotomy site to the same level (1 mm short of the sinus floor), an osteotome of diameter a little less than the planned implant body, will be inserted in the prepared osteotomy site and gently tapped to reach the same level, the osteotome will be tapped gently to fracture up the sinus floor.

**In group 2; (closed sinus lifting with densah drills):** Change the drill motor to reverse-densifying Mode (counterclockwise drill speed 800-1500 rpm with copious irrigation), Begin with the densah bur (2.5mm) until 1 mm short of the sinus floor, use the next wider Densah Bur (3.0mm) in the same mode and advance it into the previously created osteotomy with modulating pressure and a pumping motion. When feeling the haptic feedback of the drill reaching the dense sinus floor,

modulate pressure with a gentle pumping motion to advance past the sinus floor in 1 mm increments, the next wider densah drills advance in the osteotomy.

**In group 3:** The initial osteotomy will be performed with a 2-mm twist drill to remove the cortical bone, then the intralift tips (Intralift; TKW1, TKW2, TKW3, TKW4, TKW5; Satelec). TKW1 to TKW4 tips have diameters of 1.35 mm, 2.1 mm, 2.35 mm, and 2.8 mm and will be used to gradually widen the access canal to the Schneider membrane, gentle pressure will be applied on the tips to deepen the pathway, and a sterile spray (80 mL/min) cooling the tips to avoid heat injury. The TKW5 tip will be then inserted into the access canal, and the ultrasonic activation for 5 seconds with internal irrigation of 40 mL/min and repeated at 50 mL/min and then 60 mL/min. The sinus membrane will be pushed upward by the hydraulic pressure, the floating of the sinus membrane will be evaluated, and then the TKW4 (Ø 2.8 mm) will be used again to widen the access canal to the sinus membrane before plugging the bone graft.

**For all groups:** Clinical check for membrane still intact, blocking the patient's nostrils and asking the patient to blow through his or her nose. Xenograft will be added as the grafting material and pushed to the sinus through the osteotomy site until the desired height of sinus elevation will be gained, the implant fixture will be inserted. Smart peg will be placed on implant and Ostell will be used to record ISQ. Cover screw will be placed on implant and flab will be sutured. Sutures will be removed after 10 days.

## **Evaluation**

Patients will be evaluated clinically and radio graphically as follows:

1. Clinical parameter including:
  - i. Implant primary stability will be evaluated by resonance frequency analysis (RFA)  at base line.
  - ii. Implant secondary stability will be evaluated by resonance frequency analysis (RFA)  at 6 months (immediately before loading).
2. Radiological assessment:
  - i. Preoperative Cone beam computerized tomography (CBCT) will be taken for assessment of bone height and thickness (implant treatment plan) and at time of loading (6 months) to evaluate vertical bone gain, ridge width, crestal bone loss and bone density.

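### The plan does not require, or state, that CBCT scans are read without knowledge of the treatment group, although every bone outcome is taken from CBCT

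*Protocol*

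**What the plan says.** The protocol labels the design only as "Comparative study" and, under Intervention, states that "The patients will be randomly divided into 3 equal groups". It describes no masking in either place.

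The Evaluation section begins "Patients will be evaluated clinically and radio graphically as follows". Its radiological part calls for a CBCT before surgery and another "at time of loading (6 months) to evaluate vertical bone gain, ridge width, crestal bone loss and bone density". It does not say who reads the scans, how many readers there are, or what they know about the patient.

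The sample size section ties the trial's size to one of these readings: "According to analyses of the post-operative bone height", with "an alpha-type error of 0.05, a power test of 0.95, a total sample of at least 21 subjects (7 subjects for each group".

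The SAP reports the CBCT outcomes in Tables 4 to 12 and is equally silent on the reader. The protocol's description of the setting names the "Department of Oral Medicine, Periodontology, Oral Diagnosis and Oral Radiology", but only as the place from which patients are drawn.

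**The concern.** The surgeon must know the technique. The person who measures the scan need not. If that person knows the group, small consistent differences in where a landmark is placed can move one group relative to the others. Randomisation does not remove this, because the error enters after treatment.

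Height, gain, width, crestal loss and density all come from the same scans, so they share the exposure. The positive between-group bone result is a difference of 1.1 to 1.2 mm in gain, with 7 patients per group. Implant stability is a device reading and is outside this point.

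**Working it through.** **Inputs.** SAP Table 6, bone gain in mm, mean (SD), n = 7 each: Densah 5.81 (0.51), Piezo 5.72 (0.44), Osteotome 6.93 (0.45). The SAP specifies Bonferroni pairwise tests after ANOVA, at a significance level of 0.05.

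**1. Reproduce the reported result.**
- Pooled variance = (0.51² + 0.44² + 0.45²)/3 = 0.6562/3 = 0.2187, so the pooled SD is 0.468 mm.
- Within-group sum of squares = 6 × 0.6562 = 3.937. Between-group sum of squares = 7 × (0.343² + 0.433² + 0.777²) = 6.36, using deviations from the grand mean of 6.153.
- F(2,18) = (6.36/2)/0.2187 = 14.5, P = 0.0002. Eta squared = 6.36/(6.36 + 3.94) = 0.618.
- The SAP reports P < 0.001 and 0.617, so Table 6 is reproduced.

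**2. Smallest difference that is significant after Bonferroni.**
- SE of a difference = 0.468 × √(2/7) = 0.250 mm.
- Critical t (18 df, two-sided 0.05/3) = 2.639.
- Critical difference = 2.639 × 0.250 = 0.66 mm.

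**3. Reading shift in favour of Osteotome that would remove significance.**

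| Contrast | Observed (mm) | Minus critical difference | Tipping shift (mm) |
|---|---|---|---|
| Osteotome − Densah | 6.93 − 5.81 = 1.12 | 1.12 − 0.66 | 0.46 |
| Osteotome − Piezo | 6.93 − 5.72 = 1.21 | 1.21 − 0.66 | 0.55 |

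Losing the overall P < 0.05 takes a shift of about 0.59 mm.

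**4. The same check on six-month height (Table 4), the kind of outcome used for sizing.**
- Pooled SD = √[(0.59² + 0.49² + 0.53²)/3] = √0.2897 = 0.538 mm. This gives eta squared 0.551, against 0.550 reported.
- Critical difference = 2.639 × 0.538 × √(2/7) = 0.76 mm.
- Tipping shifts: (11.61 − 10.47) − 0.76 = 0.38 mm, and (11.61 − 10.41) − 0.76 = 0.44 mm.

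**5. Smaller shifts, if the techniques were truly equal.** A constant shift b in one group gives the F test a noncentrality of 7 × [(2b/3)² + 2(b/3)²]/0.468². The values of b are assumptions; the documents give none.

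| Assumed shift in one group (mm) | Actual error of the nominal 5% overall test |
|---|---|
| 0.1 | 6.4% |
| 0.2 | 10.9% |
| 0.3 | 19.0% |
| 0.5 | 46.1% |

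Masked reading enters no sample-size formula, so the total stays at 21.

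**The case against.** The case against making much of this has real content.

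- **Silence is not evidence of unmasked reading.** A reader might infer that the scans were read with the group known. The documents do not say so; they say nothing. That a person placed the landmarks is also inferred, and how density was obtained is not described. What stands is that no safeguard is required or reported.
- **A tipping point is not a bias estimate.** A reader might infer that the Osteotome advantage is an artefact. The documents do not support that. A shift of 0.46 mm is about one pooled SD and about 41% of the 1.12 mm contrast. Baseline heights are almost identical (4.66, 4.70 and 4.68 mm, P = 0.982), so a shift would have to arise almost wholly in the six-month readings. The result also favours the control group, so a reader who preferred the newer techniques would have shrunk it.
- **The other bone outcomes show no group difference.** Width, width change, crestal loss and density are not significant between groups, so the tipping shifts concern height and gain only.
- **Masking may not be free or complete.** It is tempting to say that it costs nothing because the department includes oral radiology. The protocol does not say who operates or who reads, so this cannot be concluded. An operator who also reads may recognise cases among 21 patients, especially as the preoperative scan serves treatment planning.

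These limits narrow the point to an unstated safeguard that is cheap to add. They do not remove it: unknown direction is a reason to mask, and the false-positive rate already doubles at an assumed shift of 0.2 mm.

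**Conclusion.** The concern holds in this form: neither document requires or states group-masked reading of CBCT, the source of every bone outcome and of the outcome used for sizing. The main bone-gain contrasts would lose Bonferroni significance with a differential reading shift of about 0.46 mm (Densah) or 0.55 mm (Piezo).

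This assumes a constant shift in the Osteotome group relative to the comparator, unchanged SDs, and the rounded summary figures in Table 6. It does not show that readings were unmasked, that they were biased, or that the reported difference is wrong. Some introductory pages were not available to check.

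It is an improvement that should be made, not a fault that invalidates the trial.

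**What to change.** Amend the protocol's Evaluation section to say that:

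1. CBCT scans are exported under random codes with name and group removed. There are 21 × 2 = 42, assuming one baseline and one six-month scan per patient and no losses.
2. The existing reader, preferably department staff not involved in the surgery, measures height, width, crestal level and density in random order.
3. The measurement file is locked before the group code is merged.

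Because the SAP already reports results, the sponsor should also state who read the scans and whether the group was masked. If it was not, re-read the stored scans as above and rerun the CBCT analyses in Tables 4 to 12.

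**Cost:** a few hours of coding and re-reading, with no extra patients, visits or scans.

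**Limits:** masking may be incomplete if the reader also operated. The visit cannot be masked, because the implant is visible at six months. Masked reading addresses measurement only; it does not address the operator's choice, with the technique known, of how far the sinus is elevated (protocol, Surgical Procedure, text for all groups).

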Statistical Analysis

Numerical data were explored for normality by checking the distribution of data and using tests of normality (Kolmogorov-Smirnov and Shapiro-Wilk tests). All data showed normal (parametric) distribution except for changes in bone width, crestal bone loss as well as bone density data which showed non-normal (non-parametric) distribution. Parametric data were presented as mean, standard deviation (SD) values while non-parametric data were presented as median and range values. For parametric data; two-way repeated measures ANOVA test was used to compare between the groups as well as to study the changes by time within each group. One-way ANOVA test was used to compare between mean age values in the three groups. Bonferroni's post-hoc test was used for pair-wise comparisons when ANOVA test is significant. For non-parametric data; Kruskal-Wallis test was used to compare between the three groups. Wilcoxon signed-rank test was used to compare between bone density values at base line and after six months. Gender data were presented as frequencies and percentages. Fisher's Exact test was used to compare between the three groups. The significance level was set at $P \leq 0.05$. Statistical analysis was performed with IBM SPSS Statistics for Windows, Version 23.0. Armonk, NY: IBM Corp.

Results

I. Demographic data

There was no statistically significant difference between gender distributions in the three groups. There was also no statistically significant difference between mean age values in the three groups.

Table 1: Descriptive statistics and results of Fisher's Exact test and one-way ANOVA tests for comparisons between demographic data of the three groups

Demographic data	Densah (n = 7)	Piezo (n = 7)	Osteotome (n = 7)	P-value
Gender [n, (%)]				
Male	2 (28.6%)	3 (42.9%)	4 (57.1%)	0.854
Female	5 (71.4%)	4 (57.1%)	3 (42.9%)	
Age [Mean, SD]	50.7 (5.6)	49.3 (7.2)	50.1 (7.7)	0.927

*: *Significant at $P \leq 0.05$*

II. Implant stability (RFA)

a. Comparison between groups

At base line; there was a statistically significant difference between mean implant stability measurements in the three groups. Pair-wise comparisons between groups revealed that Densah showed the statistically significantly highest mean implant stability. Osteotome showed statistically significantly lower mean value. Piezo showed the statistically significantly lowest mean implant stability.

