After six months; there was a statistically significant difference between mean bone height measurements in the three groups. Pair-wise comparisons between groups revealed that Osteotome showed the statistically significantly highest mean bone height measurement. There was no statistically significant difference between Densah and Piezo; both showed the statistically significantly lowest mean bone height measurements.

Table 4 : Descriptive statistics and results of two-way repeated measures ANOVA test for comparison between bone height measurements (mm) in the three groups

Time	Densah (n = 7)		Piezo (n = 7)		Osteotome (n = 7)		P-value	Effect size (Partial Eta squared)
	Mean	SD	Mean	SD	Mean	SD		
Base line	4.66	0.37	4.7	0.45	4.68	0.26	0.982	0.002
6 months	10.47 ^B	0.59	10.41 ^B	0.49	11.61 ^A	0.53	0.001*	0.550

*: Significant at $P \leq 0.05$, Different superscripts in the same row are statistically significantly different

b. Changes within each group

In all groups; there was a statistically significant increase in bone height after six months.

Table 5 : Descriptive statistics and results of two-way repeated measures ANOVA test for comparison between bone height measurements (mm) at different time periods within each group

Time	Densah (n = 7)		Piezo (n = 7)		Osteotome (n = 7)	
	Mean	SD	Mean	SD	Mean	SD
Base line	4.66	0.37	4.7	0.45	4.68	0.26
6 months	10.47	0.59	10.41	0.49	11.61	0.53
P -value	<0.001*		<0.001*		<0.001*	
Effect size (Partial Eta squared)	0.984		0.983		0.988	

*: Significant at $P \leq 0.05$

[figure not shown]

Figure 2 : Bar chart representing mean and standard deviation values for bone height measurements in the three groups

c. Comparison between amounts of bone gain in the three groups

After six months; there was a statistically significant difference between mean amounts of bone gain in the three groups. Pair-wise comparisons between groups revealed that Osteotome showed the statistically significantly highest mean bone gain. There was no statistically significant difference between Densah and Piezo; both showed the statistically significantly

lowest mean bone gain measurements.

Table 6 : Descriptive statistics and results of one-way ANOVA test for comparison between bone gain (mm) in the three groups

Densah (n = 7)		Piezo (n = 7)		Osteotome (n = 7)		P-value	Effect size (Eta squared)
Mean	SD	Mean	SD	Mean	SD		
5.81 ^B	0.51	5.72 ^B	0.44	6.93 ^A	0.45	<0.001*	0.617

*: Significant at $P \leq 0.05$

[figure not shown]

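### Table 2 reports Piezo and Osteotome baseline stability as different, which the SAP's stated Bonferroni test does not support; Holm would support it, but belongs here only as a labelled sensitivity analysis

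*SAP*

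**What the plan says.** The Statistical Analysis section of the SAP states that Bonferroni's "post-hoc test was used for pair-wise comparisons when ANOVA test is significant". The significance level is 0.05, and no step-down variant is named. The protocol (Intervention) says "The patients will be randomly divided into 3 equal groups", so each ANOVA has three pairs behind it. The sample size section gives "a total sample of at least 21 subjects (7 subjects for each group".

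Four ANOVA comparisons in the SAP are significant and go on to pairs: implant stability at baseline and at 6 months (Table 2), bone height at 6 months (Table 4) and bone gain (Table 6). Pairwise results appear only as superscript letters and sentences such as "Pair-wise comparisons between groups revealed that Osteotome showed the statistically significantly highest mean bone gain". No adjusted pairwise p-value is printed. For baseline stability, Table 2 gives Densah A, Osteotome B and Piezo C, and the text describes all three as significantly different from one another.

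**The concern.** There are two linked issues.

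**Efficiency.** If three means are not all equal, at most one of the three pairs can be truly equal. Multiplying every p-value by 3 then spends at most 0.05/3 = 1.67% on that pair. Holm multiplies the smallest p by 3, the next by 2 and the last by 1. It keeps the 5% ceiling under the same assumptions. With 7 patients per arm, the power lost at this step is not trivial.

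**Consistency.** The choice between the two methods decides one printed result, and that result is reported the way Bonferroni does not allow. With letters only, a reader cannot see this. What is at stake is the reported three-way ranking of primary stability, part of the protocol's stated objective.

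**Working it through.** **Inputs** (SAP Tables 2, 4 and 6; n = 7 per arm; order Densah, Piezo, Osteotome; mean and SD):
- Stability, baseline: 85.4 (4.4), 63.7 (5.1), 69.1 (4.3)
- Stability, 6 months: 78.9 (4.1), 71 (6.1), 71.9 (3.6)
- Height, 6 months: 10.47 (0.59), 10.41 (0.49), 11.61 (0.53)
- Gain: 5.81 (0.51), 5.72 (0.44), 6.93 (0.45)

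**Step 1: reproduce the SAP's own ANOVA figures.** MSE is the mean of the three variances, on 18 df.

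| Comparison | MSE | p, rebuilt | p, SAP | Eta squared, rebuilt | Eta squared, SAP |
|---|---|---|---|---|---|
| Stability, baseline | 21.29 | <0.001 | <0.001 | 0.823 | 0.822 |
| Stability, 6 months | 22.33 | 0.011 | 0.011 | 0.395 | 0.395 |
| Height, 6 months | 0.2897 | 0.0007 | 0.001 | 0.551 | 0.550 |
| Gain | 0.2187 | 0.0002 | <0.001 | 0.618 | 0.617 |

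The match shows that the summary data and this error term are adequate for the pairs.

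**Step 2: pairwise tests.** t = difference / sqrt(2 × MSE / 7), two-sided, 18 df.

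| Comparison | Pair | Unadjusted p | Bonferroni | Holm | SAP letters differ? |
|---|---|---|---|---|---|
| Stability, baseline | Densah–Piezo | <0.0001 | <0.0001 | <0.0001 | yes |
| | Densah–Osteotome | <0.0001 | <0.0001 | <0.0001 | yes |
| | Piezo–Osteotome | 0.042 | **0.126** | **0.042** | **yes** |
| Stability, 6 months | Densah–Piezo | 0.0058 | 0.017 | 0.017 | yes |
| | Densah–Osteotome | 0.0126 | 0.038 | 0.025 | yes |
| | Piezo–Osteotome | 0.726 | 1 | 0.73 | no |
| Height, 6 months | Piezo–Osteotome | 0.0006 | 0.002 | 0.002 | yes |
| | Densah–Osteotome | 0.0009 | 0.003 | 0.002 | yes |
| | Densah–Piezo | 0.837 | 1 | 0.84 | no |
| Gain | Piezo–Osteotome | 0.0001 | 0.0004 | 0.0004 | yes |
| | Densah–Osteotome | 0.0003 | 0.0009 | 0.0006 | yes |
| | Densah–Piezo | 0.723 | 1 | 0.72 | no |

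Bonferroni reproduces 11 of the 12 printed decisions. Holm reproduces all 12, and so do unadjusted tests.

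**Step 3: the exception in detail.** SE = sqrt(2 × 21.29 / 7) = 2.466; t = (69.1 − 63.7) / 2.466 = 2.19; p = 0.042; × 3 = 0.126.
- Rounding of the printed figures moves the Bonferroni value only between 0.11 and 0.14.
- The Bonferroni critical t on 18 df is 2.639, so a difference of 2.639 × 2.466 = 6.51 was needed, against 5.4 observed.
- Equivalently, MSE would have to be at most 3.5 × (5.4 / 2.639)² = 14.65. With a between-group sum of squares of 7 × 255.24 = 1786.7, eta squared would then be 1786.7 / (1786.7 + 18 × 14.65) = 0.871, against the printed 0.822.

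So neither rounding nor a smaller error term explains the letters.

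**Step 4: Bonferroni against Holm in general.** Simulation with 400,000 trials per scenario, n = 7 per arm, normal data with equal variances, and pairs tested only after a significant ANOVA. The protocol gives no planning effect size, so the spacings are assumptions.

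| Scenario | Quantity | Bonferroni | Holm |
|---|---|---|---|
| All three equal | family-wise error | 4.2% | 4.2% |
| One pair equal, third arm far away | family-wise error | 1.7% | 5.0% |
| One arm 1.5 SD away | both true pairs found | 0.43 | 0.50 |
| One arm 2.0 SD away | both true pairs found | 0.77 | 0.82 |
| Means 0, 1.5, 3 SD | all three pairs found | 0.29 | 0.53 |

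**The case against.** Bonferroni is valid and conservative, and the SAP is written in the past tense with full results. Moving to a more liberal procedure now, when its only effect on the 12 pairs is to take one p-value from 0.126 to 0.042, would be a results-driven change. This stands, and it rules out replacing the main method in this report.

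Only the 5% ceiling is shared. Holm's actual error rises from about 1.7% to about 5% when one pair is truly equal. This also stands: the extra power uses error allowance that Bonferroni leaves unspent.

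Holm is not the only alternative. With exactly three groups and a significant one-way ANOVA, unadjusted pair tests at 0.05 also hold about 5% (simulated 4.9% to 5.0%) and find more: both true pairs 0.62 at 1.5 SD and 0.90 at 2.0 SD. So Holm is one reasonable choice among valid ones. That does not rescue the stated method's mismatch with Table 2.

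A reader might infer that Bonferroni cost this trial a true finding which Holm would recover. The documents do not support that: the one pair that Holm adds is already printed as significant. A reader might also infer that the analysis really used Holm, or no adjustment. Both fit all 12 letters, so the tables cannot tell them apart, and a plain error in the letters is equally possible.

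Finally, Holm works within one outcome. It does nothing about the several outcomes and time points each tested at 0.05.

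**Conclusion.** The concern holds in a limited form. The stated Bonferroni step is valid but uniformly less powerful than Holm at the same 5% ceiling; in the assumed scenarios with one arm apart, the chance of finding both true pairs differs by 0.05 to 0.07. In this report the choice affects one of 12 pair decisions: Piezo versus Osteotome stability at baseline. That pair is reported as different, although the stated method gives 0.126. Method text and table must be reconciled.

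The conclusions on 6-month stability, bone height and bone gain are the same under either method. Bone width and baseline height are not involved, because their between-group ANOVAs were not significant (0.990 and 0.946; 0.982).

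This rests on the printed means and SDs, 7 patients per arm, two-sided tests and an error term pooled over the three arms. The agreement with the printed ANOVA results supports that error term. The power figures rest on the assumed spacings and on normal data.

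**What to change.** 1. Re-run the pairwise tests from the patient data. Print Bonferroni-adjusted p-values beside the letters for stability at both visits, 6-month height and bone gain (12 values).
2. Under the stated method, give Piezo and Osteotome the same letter for baseline stability in Table 2, and change the text to say that these two groups were not significantly different. If another procedure produced the letters, disclose which one.
3. Add Holm-adjusted p-values as a dated sensitivity analysis, labelled as chosen after the results were known.
4. In a future plan fixed before results are seen, a suitable sentence would be: *When the ANOVA is significant, the three pairwise comparisons use the pooled error term with Holm-adjusted p-values.*

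The cost is a short re-run, one extra column and one corrected sentence, with no extra patients. There are two downsides. One printed baseline ranking loses support under the stated method. Holm also has no simple matching simultaneous confidence intervals, though none are reported here.
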